### 6.8.1 Prophylaxis

For cytotoxic chemotherapies, allopurinol administration is recommended 24 hours prior to initiation of treatment with SUPLEXA because of the immediate action of the cytotoxic chemotherapy. For cellular therapies however, cells require at least a day to migrate out of the circulation to the tumour bed and synchronous tumour lysis will be delayed. Therefore, allopurinol will be administered concomitantly with each SUPLEXA dose, and between doses as directed by the investigator.

The following pretreatment regimen is suggested, although a different regimen based on local standard of care/ institutional practices is permitted: Approximately 1 hour (60 min  $\pm$  15 min) before each SUPLEXA infusion, all subjects will receive single administration of:

- Acetaminophen 1000 mg PO (for potential fever)
- Diphenhydramine 12.5 mg PO (for potential rash)
- Allopurinol 100 mg (IV or PO) (for potential tumour lysis syndrome in subjects who are at intermediate risk for TLS; refer to [Figure 6](#)). This should be followed, unless the investigator determines continued oral dosing of allopurinol is required.

### 6.8.2 Prohibited Medications and Treatment

Medications or vaccinations specifically prohibited in the exclusion criteria are not allowed during the ongoing study. If there is a clinical indication for any medication or vaccination specifically prohibited during the study, discontinuation from study intervention may be required. The Investigator should discuss any questions regarding this with the Sponsor's Medical Monitor. The final decision on any supportive therapy or vaccination rests with the Investigator and/or the subject's primary physician. However, the decision to continue the subject on study intervention requires the mutual agreement of the Investigator, the Sponsor, and the subject. Subjects who, in the assessment of the Investigator, require the use of any of the prohibited treatments for clinical management should be removed from the study.

The following medications are excluded from concomitant use for all subjects during the study:

- Vaccines:

- Live vaccines including, but are not limited to measles, mumps, rubella, varicella/zoster, yellow fever, rabies, *Bacillus Calmette–Guérin* (BCG), and typhoid vaccine.
- Attenuated vaccines, e.g., FluMist®
- Inactivated vaccines, e.g., COVID-19 vaccine; Please also refer to Section 10.9 (Guidance to Address Global Health Emergencies)
- Research vaccines, including any investigative COVID-19 vaccine studies

Note: Seasonal influenza vaccines for injection are generally killed virus vaccines and are allowed.

- Concurrent use of immunostimulatory agents, including but not limited to IFN- $\alpha$ , IFN- $\gamma$ , or interleukin 2 (IL-2) with study intervention, during the entire study.
- Any investigational agent, other than SUPLEXA.
- Immunosuppressive anticancer therapies (chemotherapy, radiation therapy, biological therapy or immunotherapy which are not specified in this protocol) or approved by the Sponsor will be excluded. Herb supplements that are used for the treatment of the malignancy under the study are not allowed.

Note: Palliative radiation therapy for pain management or for symptomatic solitary lesion if not new lesion may be allowed at the Investigator's discretion.

*Note: Surgery to bone lesion to prevent the risk of fracture will be allowed.*

- Concurrent use of immunosuppressive medications, including but not limited to cyclophosphamide, azathioprine, or methotrexate.

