### 7.2 DISCONTINUATION OF STUDY INTERVENTION

In some instances, it may be necessary for a subject to permanently discontinue study intervention. Please also refer to stopping rules described in Section [7.1](#).

A subject must permanently discontinue study intervention if they meet one of the following individual stopping rules:

- Any Grade 4 life threatening events assessed as related to study intervention.
- $\geq$ Grade 3 immunological-related event assessed as related to study intervention (refer to Section [7.2.1](#))

A subject may also discontinue study intervention for reasons including but not limited to:

- Adverse event
- Lost to follow-up
- Non-compliance with study drug
- Physician decision
- Pregnancy (refer to Section [7.2.2](#))
- Progressive disease
- Protocol deviation
- Study terminated by Sponsor
- Withdrawal by subject
- Death

Permanent discontinuation of study intervention does not mean withdrawal from the study, and the subject will be encouraged to remain in the study, complete the ET visit and then continue to complete all study visits as per the SoA, including all follow-up visits.

For subjects who have discontinued study intervention due to reasons other than disease progression, tumour assessment will be continued at the protocol-specified schedule until documented disease progression or initiation of subsequent anticancer therapy or until 24 months after the last dose of study intervention.

The primary reason for discontinuation from study intervention should be documented on the appropriate eCRF.

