## 10.7 APPENDIX 7: CRS TOXICITY TREATMENT GUIDELINES

Note these as guidelines may require modification based on clinical circumstances of each subject. The investigator should consider both best outcome for the subject and institutional standard of care treatment protocols. As such failure to exactly follow these guidelines is not a protocol deviation or violation as follows:

Cytokine Release Syndrome Grading Assessment (Lee, 2019)	Corticosteroids
Grade 1: Symptoms are not life-threatening and require symptomatic treatment only (fever, nausea, fatigue, headache, myalgias, malaise)	
 
• N/A
 

Grade 2: Symptoms require and respond to moderate intervention: 
 
• Oxygen requirement <40% FiO2 OR
 
• Hypotension responsive to IV fluids or low dose of one vasopressor OR
 
• Grade 2 organ toxicity*
 
	
 
• Vigilant supportive care with careful monitoring of cardiac and other organ function
 

Grade 2: As above but with extensive co-morbidities or older age. OR Grade 3: Symptoms require and respond to aggressive intervention: 
 
• Extensive co-morbidities or older age
 
• Oxygen requirement <math>\geq 40\%</math> FiO2 OR
 
• Hypotension requiring high-dose or multiple vasopressors OR
 
• Grade 3 organ toxicity* or Grade 4 transaminitis
 
	
 
• Administer methylprednisolone 1 mg/kg IV twice daily or equivalent dexamethasone (e.g., 10 mg IV every 6 hours). Continue corticosteroids use until the event is Grade 1 or less, then taper over 3 days.
 
• If no improvement, within 24 hours, consider starting tocilizumab or manage as Grade 4 (below)
 

Grade 4: Life-threatening symptoms: 
 
• Requirement for ventilator support OR
 
• Grade 4 organ toxicity* (excluding transaminitis)
 
	
 
• Administer methylprednisolone 1000 mg IV per day for 3 days; if improves, then manage as above.
 
• Consider alternate immunosuppressants if no improvement or if condition worsens.
 

Source: (Lee, 2019) (EMA, 2018)

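### Section 6.8.2 gives two incompatible consequences for needing a prohibited medication; for drugs that are not anti-cancer therapy, removal from the study also conflicts with Sections 6.5.1, 7.2 and 7.3

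*Combined protocol and SAP*

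**What the plan says.** Three sentences in the first paragraph of Section 6.8.2 matter here. The first is permissive: "If there is a clinical indication for any medication or vaccination specifically prohibited during the study, discontinuation from study intervention may be required". The second lets a subject stay on SUPLEXA if the Investigator, the Sponsor and the subject all agree. The third says that subjects who, in the Investigator's assessment, "require the use of any of the prohibited treatments for clinical management should be removed from the study".

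The list that follows applies to all subjects during the study. It covers most vaccines, immunostimulants, other investigational agents, immunosuppressive anti-cancer therapies and, as a separate item, "Concurrent use of immunosuppressive medications, including but not limited to cyclophosphamide, azathioprine, or methotrexate".

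Other sections bear on the same subjects:

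- Section 7.2 requires SUPLEXA to stop for "Any Grade 4 life threatening events assessed as related to study intervention". It adds that "Permanent discontinuation of study intervention does not mean withdrawal from the study", and that for subjects who stop for reasons other than progression, "tumour assessment will be continued at the protocol-specified schedule until documented disease progression", a new anti-cancer therapy or 24 months after the last dose.
- Section 6.5.1 keeps subjects who stop because of a DLT in follow-up, with an exception for consent withdrawal and other anti-cancer therapy.
- Section 7.3 lists starting a prohibited medication as a possible reason for withdrawal, and specifies anti-cancer treatment in parentheses.
- Section 4.1.3 withdraws subjects who begin new anti-cancer therapy.
- Appendix 7 (Section 10.7) advises, for Grade 4 CRS: "Consider alternate immunosuppressants if no improvement or if condition worsens".

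**The concern.** A site facing this situation gets two instructions. One allows continued dosing, or a stop to dosing with follow-up. The other takes the subject out of the study. The protocol draws no line between a clinical indication for a prohibited drug and a requirement for one, so the wording does not tell the site which rule governs.

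The choice matters because safety is the primary objective of this first-in-human trial. Subjects who need unusual supportive treatment are among those whose later course is of most interest. If the removal sentence is followed, scheduled examinations, laboratory tests and tumour assessments end for reasons linked to the subject's clinical state. Time to progression and PFS are then censored at the last tumour assessment (Section 9.3.2).

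**Working it through.** The plan states no figure on this point, so the check is a comparison of text followed by simple counts.

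**Step 1: the two consequences within 6.8.2.** The trigger is a clinical need for a prohibited treatment. Outcome A: SUPLEXA may be stopped, or continued by three-way agreement. Outcome B: the subject leaves the study. A subject who continues dosing cannot also have been removed.

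**Step 2: which prohibited items create a conflict with other sections.**

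- *New anti-cancer therapy.* Section 4.1.3 withdraws the subject, 7.3 lists it as a withdrawal reason, and 6.5.1 makes it part of the exception to continued follow-up. Removal is consistent.
- *Vaccines, immunostimulants and immunosuppressants that are not anti-cancer therapy.* Section 7.2 separates stopping SUPLEXA from leaving the study, 6.5.1 does the same after a DLT, and the parenthesis in 7.3 does not reach these drugs. Removal conflicts.

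**Step 3: the Grade 4 CRS case.** A related Grade 4 event stops SUPLEXA under 7.2, with the subject encouraged to complete all follow-up visits. If CRS does not improve, Appendix 7 suggests another immunosuppressant. The 6.8.2 list bars immunosuppressants in open-ended terms, with no exception for treating toxicity. On that reading the subject should be removed, against 7.2. This case is arguable (see the objection).

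**Step 4: what removal would lose, per subject.**

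*AE window.* Table 4 collects AEs, and SAEs regardless of cause, until 30 days after the last dose. Section 8.3.1 does not oblige investigators to seek events once participation ends. With removal on day *d* after the last dose, the days without active collection are 30 − *d*. The documents give no *d*, so an assumed range is shown:

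- *d* = 3: 30 − 3 = 27 days
- *d* = 7: 30 − 7 = 23 days
- *d* = 14: 30 − 14 = 16 days

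The gap is shorter if the early termination visit, due within 30 days, comes later than day *d*.

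*Scheduled visits.* Every 8 weeks for 48 weeks gives 48 / 8 = 6 visits, on days 56, 112, 168, 224, 280 and 336. The first falls 56 − 30 = 26 days after the Table 4 window closes, so these visits do not add to the AE loss above. What goes is their examination, laboratory tests and disease evaluation.

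*Scans.* Section 4.1.2.3 sets scans every 6 to 12 weeks. Over 48 weeks: 48 / 12 = 4 to 48 / 6 = 8. Over the 24 months allowed by 7.2, taken as 104 weeks: 104 / 12 = 8.7, so 8 complete intervals, to 104 / 6 = 17.3, so 17. These are ceilings for a solid-tumour subject who neither progresses nor starts new therapy.

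**Step 5: what is kept.** The triggering event itself is already recorded. Related SAEs are reportable at any time (Table 4). AEs that are serious, related or caused discontinuation are followed (8.3), SAEs to resolution or stabilization (8.3.3). Unresolved related toxicity is followed until stable (Schedule of Activities, note t). Section 4.1.3 provides contact at least every 12 weeks for OS and PFS after early withdrawal; the synopsis makes this optional. No endpoint definition, analysis set or stopping rule depends on the sentence.

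**Step 6: how many subjects.** This cannot be estimated. Section 2.3.1 reports no treatment-related AE in more than 15 subjects, so for toxicity treatment the number may be zero.

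**The case against.** The strongest reply is that the protocol, read as a whole, never intends to remove a subject for treating toxicity. Section 6.8 permits drugs for AEs, 6.8.3 calls for appropriate supportive care, 6.8.2 itself leaves the final decision on supportive therapy to the treating physicians, and 7.3 points to anti-cancer treatment. The immunosuppressant item also bars *concurrent* use. By the time a Grade 4 CRS patient reaches that step of Appendix 7, SUPLEXA has stopped for good, so there may be nothing for the drug to be concurrent with.

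Much of this stands, and it is why the CRS case is called arguable. It does not settle it. The list applies throughout the study, and the immunosuppressant item lacks the tie to study intervention that the immunostimulant item has. The sections cited show what was probably meant; they do not change what the removal sentence says. The contradiction inside 6.8.2 does not depend on the CRS case.

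The reply is also right that the loss is small. Table 4 does not name removal as the end of AE collection, and the scan counts assume a patient who never progresses.

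Three stronger readings are tempting, and the documents support none of them:

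- *Removal is wrong for every prohibited treatment.* For new anti-cancer therapy it agrees with 4.1.3, 6.5.1 and 7.3.
- *The steroids in Appendix 7, including those for Grade 2 CRS with older age or co-morbidities, trigger removal.* Section 6.8.2 does not name corticosteroids, exclusion 3 concerns chronic use, 6.6 directs sites to the CRS guidelines, and DLT item 1d presupposes steroid treatment.
- *The trial would lose its data on the worst toxicities.* The triggering event and related SAEs stay reportable and followed.

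**Conclusion.** The inconsistency is real and confined. Section 6.8.2 attaches two incompatible outcomes to one trigger. For prohibited items other than anti-cancer therapy, the removal outcome also departs from 6.5.1, 7.2 and 7.3. Whether it reaches immunosuppressants given for Grade 4 CRS depends on how *concurrent* is read.

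The effect is conditional on a site following the removal sentence. It is then limited to part of one 30-day window for new non-serious and unrelated serious events, up to six visits, and the remaining scans. The day counts rest on an assumed removal day, and the visit and scan counts are upper limits. Severity is minor; confidence is moderate.

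**What to change.** Replace the last sentence of the first paragraph of Section 6.8.2 with:

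> Subjects who require a prohibited treatment other than new anti-cancer therapy should be considered for discontinuation of study intervention and remain in AE/SAE, tumour and survival follow-up per Section 7.2; subjects who start new anti-cancer therapy are withdrawn per Sections 4.1.3 and 7.3. Drugs given to treat an AE, including Appendix 7 agents, are not a reason for removal from the study.

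The anti-cancer exception is essential. Without it, the new text would contradict 4.1.3 and the follow-up paragraph of the synopsis, which withdraw such subjects. Section 7.3 can stay as it is.

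The cost is one sentence replaced and one added. No visits are needed beyond those already scheduled, and no endpoint, analysis set or stopping rule changes.

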#### 4.1.2.3 Disease Evaluation

For subjects in the solid tumours cohort, the on-treatment radiographic assessments of chest, abdomen, and pelvis will be performed per standard of care intervals throughout the course of the study.

The first radiographic scan after receiving SUPLEXA will be performed at Week 6-12 weeks after the 1st SUPLEXA infusion and thereafter every 6-12 weeks depending on tumour type and as clinically indicated per investigator's discretion.

These scans should be available for assessment by the Sponsor, if requested. The response evaluation will be assessed by the Investigator according to RECIST v1.1 and iRECIST until unequivocal radiographic disease progression, or until the subject starts a subsequent anticancer therapy (whichever comes first). The tumour assessment (imaging) for confirmation of response should be performed no less than 4 weeks after the criteria for response are first met. All radiographic scans will be collected and held for possible future retrospective evaluation by BICR.

For subjects in the haematological malignancies cohort, disease evaluation will be conducted every 4 weeks, as clinically indicated throughout the study.

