#### Type of Subject and Disease Characteristics

##### Solid Tumours

2. Histologically or cytologically confirmed diagnosis of locally advanced or metastatic solid tumour.
3. Have 1 or more tumours measurable based on RECIST v1.1 as assessed by the local site Investigator. Radiographic scans should be obtained within 5 weeks of Screening. Lesions situated in a previously irradiated area are considered measurable if objective progression has been demonstrated following radiation to such lesions.
4. Subjects who did not attain a durable response after receiving at least one standard/approved therapies which may include chemotherapy, targeted agents, radio-, immuno- conjugates, check point inhibitors or where there is no approved therapy. This includes subjects who attained a long-term stable disease (SD), or partial response (PR) are eligible. Long term SD subjects on a checkpoint inhibitor may continue checkpoint inhibitor (CPI) therapy.  
\* Any therapies defined as immunosuppressive require a washout period of at least 4 weeks, defined as 4 weeks (28 days) prior to blood collection for SUPLEXA manufacturing and any SUPLEXA dose administration.

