## Prior Therapy

14. Prior radiotherapy within 2 weeks of start of study intervention. Subjects must have recovered from all radiation-related toxicities and not require corticosteroids (up to 4 mg/day dexamethasone or equivalent will be allowed provided dose is stable for at least 30 days prior first SUPLEXA dose and remains stable throughout the trial), and not have had radiation pneumonitis. A 1-week washout is permitted for palliative radiation ( $\leq$ 2 weeks of radiotherapy) to non-CNS disease.
15. Transfusion of blood products (including platelets or red blood cells) or administration of colony stimulating factors (CSF) (including granulocyte CSF [GCSF], granulocyte-macrophage CSF [GMCSF], or recombinant erythropoietin) within 4 weeks prior to baseline.
16. Any vaccines (live, attenuated, inactivated or research vaccines) within 30 days of dosing with study intervention (refer to Section [6.8.1](#) for prohibited vaccines).

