##### *Target Lesions:*

Target lesions are measured at every subsequent assessment and an overall SOD is calculated. Target lesions are assessed as Complete Response (CR), Partial Response (PR), Stable Disease (SD), Progressive Disease (PD), or Not All Evaluated (NAE) at every time point based on the calculated SOD.

Target Assessment	Evaluation Definition
Complete Response (CR)	CR is declared if ALL of the following are true for target lesions: 
 
• The disappearance of all non-nodal target lesions
 
• Any pathological lymph nodes must have a reduction in short axis to <10 mm.
 

Partial Response (PR)	PR is declared if there is a decrease of at least 30% in the SOD of target lesions compared to the baseline SOD of target lesions.
Progressive Disease (PD)	PD is declared if ANY of the following are true for target lesions: 
 
• SOD of all target lesions increases at least 20% compared to the smallest SOD recorded from any prior assessment                NOTE: In addition to the relative increase at least 20%, the sum must also demonstrate an absolute increase of at least 5 mm.             
 
 
OR
 
 
• The appearance of one or more new lesions.
 

Stable Disease (SD)	SD is declared if target lesion assessment does not meet criteria for PR, PD, or CR.

*Non-Target Lesions:*

While some non-target lesions may actually be measurable, they need not be measured and instead should be assessed qualitatively at subsequent assessments. Non-target lesions are assessed as CR, PD, non-CR/non-PD (NCNP), or NAE at every time point.

Non-Target Assessment	Evaluation Definition
Complete Response (CR)	CR is declared if ALL of the following are true for non-target lesions: 
 
• Disappearance of all non-target lesions and normalization of tumour marker level.
 
• All lymph nodes must be non-pathological in size (<10 mm short axis).
 

Non-CR/Non-PD (NCNP)	NCNP is declared when persistence of one or more non-target lesion(s) and/or the maintenance of tumour marker level above the normal limits is observed.

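### Palliative radiotherapy is allowed on study, but no rule says how an irradiated target lesion is analysed, so radiation shrinkage can be scored as a SUPLEXA response

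*Combined protocol and SAP*

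**What the plan says.** Section 6.8.2 lists radiation among the excluded anticancer treatments and then adds a note: "Palliative radiation therapy for pain management or for symptomatic solitary lesion if not new lesion may be allowed at the Investigator's discretion". A second note covers surgery: "Surgery to bone lesion to prevent the risk of fracture will be allowed".

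Scoring is in section 10.5.1 (Appendix 5). "Target lesions are measured at every subsequent assessment and an overall SOD is calculated", and "PR is declared if there is a decrease of at least 30% in the SOD of target lesions" relative to baseline. PD needs a rise of at least 20% and at least 5 mm over the smallest earlier sum. Table 7 (bone-only disease), Table 8 (overall response) and Table 9 (iRECIST) make no exception for a lesion treated locally during the study.

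The one rule on irradiated lesions is inclusion criterion 3, which concerns measurability at entry: "Lesions situated in a previously irradiated area are considered measurable if objective progression has been demonstrated following radiation to such lesions". The same criterion lets a subject enter with a single measurable lesion: "Have 1 or more tumours measurable based on RECIST v1.1 as assessed by the local site Investigator".

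Section 4.1.2.3 runs response evaluation to unequivocal radiographic progression, "or until the subject starts a subsequent anticancer therapy (whichever comes first"). Section 9.3.2 reports investigator-assessed ORR for unconfirmed as well as confirmed responses, and censors TTP and PFS at the last tumour assessment. It does not mention radiotherapy or surgery.

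**The concern.** Radiotherapy acts directly on the lesions that define ORR, TTP, DOR, CBR and PFS. The trial has a single arm, so no control group would show the same effect. The investigator who allows the radiotherapy also scores the response, and because unconfirmed responses are reported, one scan after radiotherapy is enough to create a responder.

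ORR and TTP are secondary endpoints. Section 9.1 lets the sample size or the cap of about 8 per tumour type grow if activity looks promising and safety is acceptable. At that size one misattributed response is visible.

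The iRECIST endpoints are open to the same problem. Under Appendix 6, stable disease or a response at the assessment after an unconfirmed progression resets the status and removes that date as the iPFS event. Irradiating the growing lesion could produce that reset.

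**Working it through.** The plan gives no figure to reproduce here: the 60 subjects and the cap of 8 come with no target ORR, alpha or power. The thresholds below are from section 10.5.1, the exact interval from section 9.3.2 and the cap from section 9.1. **Lesion sizes and shrinkage are assumptions.**

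**1. When irradiation alone gives a PR.** Let the irradiated lesion be a share w of the baseline SOD and shrink by a fraction s, with the other lesions unchanged. The SOD falls by w × s, so a PR needs s ≥ 0.30 / w.

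| Share of SOD | Shrinkage needed for PR |
|---|---|
| 100% (only target) | 30% |
| 60% | 50% |
| 50% | 60% |
| 40% | 75% |
| 33% | 90% |
| below 30% | impossible |

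Example: targets of 40 + 30 + 30 = 100 mm. If the 40 mm lesion falls to 9 mm, the sum is 69 mm (−31%), a PR. The threshold is met at 10 mm.

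**2. Masked progression.** Targets of 40 + 30 = 70 mm. The 40 mm lesion is irradiated and falls to 12 mm; the other grows to 36 mm.
- As written: 12 + 36 = 48 mm, and 48/70 − 1 = −31.4%, scored PR with no TTP event.
- Without the irradiated lesion: 30 to 36 mm is +20% and +6 mm, which meets both PD thresholds.

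**3. How much growth elsewhere is hidden.** Take equal 30 mm targets, with baseline as the smallest sum so far, and let g be the growth of the non-irradiated lesions needed for PD.
- Two lesions: 30(1 − s) + 30(1 + g) ≥ 72, so g ≥ 0.40 + s. That is 40% with no shrinkage, 90% at s = 0.5 and 120% at s = 0.8.
- Three lesions: 30(1 − s) + 60(1 + g) ≥ 108, so g ≥ 0.30 + 0.5s. That is 30%, 55% and 70%.
- With the irradiated lesion left out, 20% (and at least 5 mm) is enough.

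The masking is strongest at the first scan after radiotherapy, because the smaller sum then becomes the reference. In example 2 the reference becomes 48 mm and PD is reached at 1.2 × 48 = 57.6 mm. If the irradiated lesion stays at 12 mm, the other must reach 45.6 mm. Had the 40 mm lesion simply not changed, PD would come at 84 mm in total, with the other lesion at 44 mm. From the second scan the delay in this example is therefore small.

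**4. Effect on ORR** (Clopper-Pearson 95%).
- Tumour type of 8: 0/8 = 0% (0 to 36.9%); 1/8 = 12.5% (0.3% to 52.7%).
- All 60 subjects, as the largest possible denominator: 0/60 = 0% (0 to 6.0%); 1/60 = 1.7% (0.0 to 8.9%).

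**The case against.** The strongest reply is that section 4.1.2.3 may already close the gap. Section 6.8.2 itself names radiation among anticancer therapies, so the palliative form could be read as a subsequent anticancer therapy that ends response evaluation. That reading is fair and would remove most of the bias. It is not written, however, and the censoring rule in section 9.3.2 does not repeat it. Nor can a reader infer the opposite, that a permitted exception is certainly not such a therapy. The documents leave it open, and two analysts could score the same subject differently.

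Other points limit the concern:
- A reader might infer that only baseline lesions may be irradiated. The condition about new lesions may qualify only the solitary-lesion branch and not radiotherapy for pain. The point does not need that inference: a new lesion is already PD under Table 8, so it is treatment of baseline lesions that can distort the score.
- A reader might infer that radiotherapy between the baseline scan and the first dose is clearly uncovered, since for exclusion 14 "A 1-week washout is permitted for palliative radiation". Inclusion 3 can be read to make such a lesion non-measurable, so this is arguable.
- Section 10.5.1 refers to the published RECIST v1.1 for details, and section 9.3 says a later SAP will supersede it. Neither is available here, so what is shown is a gap in this text.
- New lesions and unequivocal non-target progression still give PD.
- Safety is the primary objective, and the expansion provision has no numerical response threshold.

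These points reduce the size of the concern. None of them supplies the missing rule.

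**Conclusion.** The concern holds in this limited form. The protocol allows radiotherapy to a target lesion, keeps that lesion in the SOD, and gives no analysis rule for it. Radiation shrinkage can then be scored as PR or CR and can hide progression elsewhere, mainly at the first scan after radiotherapy. The size depends on the lesion's share of the SOD: 30% shrinkage is enough for a sole target, while no PR is possible from a lesion below a 30% share. One such subject is worth 12.5 points of ORR in a tumour type of 8, within a wide interval.

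The conclusion assumes that permitted radiotherapy does not end response evaluation, which the documents leave undecided, and that nothing in the published criteria or the later SAP settles the scoring. A reader might infer that many responses will be affected or that progression is delayed throughout follow-up. The documents give no radiotherapy rate to support the first, and the falling reference sum argues against the second. This is a cheap improvement that should be made; it does not touch the primary safety objective.

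**What to change.** Make the change in section 9.3.2 and the SAP only. Appendix 5 scoring also feeds the treatment-continuation decisions in section 4.1.2.2, so those decisions and the radiotherapy permission should stay as they are.

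1. State whether permitted palliative radiotherapy counts as subsequent anticancer therapy for ending response evaluation (synopsis and section 4.1.2.3).
2. For analysis, treat a target lesion irradiated or resected after the baseline scan as not evaluated (NAE) from that date. Score the time point NE for every non-target combination, unless PD is shown in other lesions or by new lesions. Table 8 gives NE only for NAE with non-CR/non-PD, so the other combinations need a line. A CR or PR first met after such treatment does not count for ORR, DOR or CBR, under RECIST v1.1 or iRECIST. Disappearance of an irradiated non-target lesion does not support CR.
3. For TTP, PFS and DOR, including responders irradiated later, report two analyses: one censored at the last assessment before the radiotherapy, and one counting radiotherapy to a baseline lesion as progression. Name the main one in advance. Censoring alone may be informative if the lesion was treated because it was worsening.
4. Record the treated lesion's ID and the date in the eCRF. Section 6.8 asks for the therapy, reason, dates and dose, but not the lesion, so affected responses might not be identifiable later.

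The cost is some SAP text and a small eCRF addition. A few time points become NE, and ORR and TTP may be slightly less favourable.
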